#### 2. PROTOCOL AMENDMENTS

Any amendments have been made to the protocol.

#### **3. STUDY SUMMARY**

*Background:* Many young children with autism enter educational provision without any effective means of communicating their needs. Currently, most intervention including speech and language therapy is provided in schools. Thus, parents are rarely involved in interventions such as PECS and generalisation to the home situation is very limited. The focus of the proposed study is on helping parents of young children with autism to use PECS at home and to monitor outcome using measures that directly reflect children's spontaneous communication in the home setting.

*Overall Aim:* assess the feasibility and acceptability of teaching the use of PECS to parents and young autistic children at home.

Design: Feasibility and pilot Randomised Controlled Trial (RCT).

*Participants:* 64 young children (age between 2-10 years). Equal numbers of children will be randomised *at each school* either to: a) PECS treatment or (b) Treatment as usual (TAU) as follows: 32 children in the PECS group; 32 children in the "treatment as usual" group. (b) Treatment as usual (TAU).

## 4. BACKGROUND INFORMATION

The emergence of language is crucial for social and emotional development but it is estimated that up to 30% of individuals with autism fail to develop functional speech . Furthermore, once they reach school age, minimally verbal children show almost no gains in vocalisations or communicative exchanges over the course of a whole school year  and few develop compensatory strategies, such as gesture, to communicate basic needs. This has a significant detrimental impact on individuals and their families and increases the risk of children developing emotional and behavioural problems .

The Picture Exchange Communication System  (PECS) was specifically designed to help pre-verbal children with autism make spontaneous requests for basic needs i.e. food, play or leisure activities. Evidence for the effectiveness of PECS with children with autism is promising but limited . The few randomised controlled trials (RCTs) of PECS that have been conducted () all reported some increases in communication following training but comparisons with alternative interventions produced varying results. Thus, while PECS training resulted in greater improvements in communicative word use than Responsive Education and Prelinguistic Milieu Teaching , there were no differences in outcome compared with Pivotal Response Training . Furthermore, whilst increases in child initiations in classes where teachers were trained to use PECS were greater than among pupils receiving teaching as usual, treatment effects were not maintained when intervention ceased . Other non-RCT studies have reported improved verbal and functional communication , with possible reduction in problem behaviours  and improvement in social communication .

These studies suggest PECS can increase child-initiated communication and some generalisation of the use of PECS to untrained adults or new settings has been reported. However, in a meta-analysis  generalisation was reported in only 54% of studies and parent involvement was only included in one study . In other studies, although parent training was provided to enhance generalisation, the results were not reported . Only one small study (three mothers) has specifically investigated the delivery of PECS in the home setting, finding that this approach was both feasible and acceptable to parents . Nevertheless, it is also evident, from an analysis of YouTube videos of parent-led PECS exchanges , that the standard of home-based delivery is often inconsistent and is characterised by a high proportion of implementation errors.

In summary, most high quality PECS research to date has been conducted by trained professionals in clinical or education settings  rather than at home, despite the fact that this is where children spend a significant proportion of their time. Moreover, the use of PECS in schools is often restricted to snack times, in which requests are cued by the situation rather than being truly spontaneous and unprompted . This is contrary to the principles of PECS, which, at least in the early stages, require that rewards are provided immediately after every spontaneous request. Although in schools this is impractical, in the home environment spontaneous requests to parents can be rewarded immediately and positively. The NICE Clinical Guideline  recognised the importance of research to improve communication skills in children and young people with autism, specifically highlighting the need to determine whether PECS is "effective in improving spontaneous requesting in nonverbal children with autism across a range of contexts that demonstrate generalisation of skills". In 2015, the James Lind Alliance survey , funded by a collection of charities headed by Autistica, identified communication as the second most important area requiring research. Furthermore early intervention for children with disability is a priority in Improving Children and Young People's Health Outcomes . This study aims to establish the requirements for a high quality investigation of PECS intervention and is specifically designed to evaluate its impact on communication in the home setting, for young non-verbal autistic children.

# 5. METHODS

## 5.1 STUDY AIMS AND DESIGN:

This Feasibility and pilot randomised controlled trial (RCT) aims to:

- a) Evaluate the feasibility and acceptability of teaching the use of PECS to parents and young autistic children at home
- b) Test the feasibility of using Early Years and special school education services to recruit young children with autism in the London area
- c) Pilot and assess the use of an App designed to enable parents accurately and easily to count and rate their child's spontaneous requesting in the home context
- d) Test the feasibility and acceptability of using small body cameras (worn by the child) to gather direct observational data on communication behaviours at home.

- e) Provide pilot data, including estimates of retention rate, assessment completion and effect size, in order to prepare an application for a large multi-site RCT of home-based PECS training for parents of non-verbal young children with autism in the UK.
- f) Conduct a short term follow-up, 4 weeks after the cessation of training, to monitor the continuing use of PECS at home and any sustained progress made by the child.

## **5.2 PARTICIPANTS**

The present feasibility study will focus on young children (between 2 and 10 years of age) since our aim is to explore the possibility of establishing strong independent and functional communication skills as early as possible. A total of 64 young children (N=64) will be recruited in the study.

Inclusion criteria:

- Child: age between 2 and 10 years
- Clinical diagnosis of autism spectrum disorder and meeting cut-off for autism symptoms (i.e. ≥15 on the Social Communication Questionnaire)
- Non/minimally verbal (i.e. fewer than 10 words used on a regular basis)
- Parents willing to consent to participation and able to engage in intervention at home.

*Exclusion criteria*: Children who have more than 10 words used regularly; have severe visual impairment; have a twin brother or sister. Parents with reduced levels of spoken and/or understanding of English, which would limit participation.

## **5.4 RECRUITMENT**

Participating schools have been approach via the Pan London Autism Schools Network (PLASN). This network was established in 2009 with the collaboration of Autism Speaks and the Institute of Education (UCL), [name], Principal is a co-founder of the group which currently comprises twelve specialist schools. PLASN schools have developed strong links with local universities to focus on research issues that are of particular relevance to staff, pupils and families in the network. The collaboration has previously contributed to a number of research studies involving several of the applicants. All children in PLASN schools have a Statement of Special Educational Needs (SEN) and/ or Education Health and Care Plan (EHCP) with autism as their primary need.

The study team will send an invitation letter to the schools (these schools are part of the PLASN). The contact details of the research team will be included in the letter. Any questions the schools may have will be answered by a member of the research team in person or via email/telephone.

Prior to randomisation, the mobile telephone number of the research assistant will be provided to facilitate arrangements for assessments. Because the research assistant will be blinded to the group allocation, the mobile telephone number of a member of the study team who is not blinded to the group allocation will be provided to the parents after they are randomised to groups. This will prevent any inadvertent information about group allocation being divulged to the research assistant and is consistent with the study design. Mobile telephone numbers provided to participants will be specifically designated for the study.

If the schools are interested in participating, the research assistant and/or the chief investigator will visit the school to meet the senior school collaborators and will give them the information sheet in person (School IS V1 27.08.19). In addition they will discuss the study in detail and establish the criteria for participation to ensure that only families who meet these criteria are informed about the study. If the schools are happy to take part, they will be asked to sign a written agreement (Schools MOA V1 27.08.19) outlining the details of their participation and to send it back to the research team via email or post. This will email will not contain any confidential information about study participants. Alternatively, a member of the research team will collect the signed agreement in person at the school.

School staff will inform parents about the study and will provide them with the Parent Information Sheet (Parent IS 27.08.19) which has contact details of the study team. Parents will be invited to complete a section of the form indicating their agreement or refusal to be contacted by the research assistant. In order to make the process easier for the families they will be asked to return the slip to the school in a sealed envelope (provided by the research team) in the child's school bag. Envelopes will be stored in an agreed location at the school e.g. in the main office so that a member of the study team can collect them at an agreed date. School staff will be asked to remind parents about the request only once to prevent any risk of undue pressure. Afterwards, the research assistant ([name]) will contact the interested families via telephone or email and provide full details about the study. Parents will be told that their participation in the study is voluntary and additional to the school curriculum. Also that they will be able to withdraw at any point during the duration of the project (i.e. until the 10th of December 2021). [name] will send parents a blank consent form via email or post. Parents will have two weeks to decide if they wish to take part. Parents will be asked to sign the consent form and send it back to the research team via encrypted email or confidential post. Alternatively, parents can give the signed consent form to the study team in person. All parents will be invited to attend a half-day educational workshop hosted at the school and delivered by [name] or [name] and the research therapist [name]. Parents will be provided with information about autism, communication, behaviour, other relevant issues and general information about local resources.

The decision as to whether a child will participate in the study will rest with their parent. Children who meet eligibility criteria for participation in the study will have severe autism, significant learning disability, little or no verbal communication and in all likelihood very limited comprehension. The developmental age equivalent of children eligible for the study is likely to be below 18 months of age and they therefore, lack capacity to assent to participation in the study.

Eligibility criteria are provided below for information: a) age 2-10 years b) with a clinical diagnosis of autism spectrum disorder and meeting cut-off for autism symptoms (i.e. ≥15 on the Social Communication Questionnaire) and c) non/minimally verbal (i.e. fewer than 10 words used on a regular basis).

## 6. ASSESSMENTS (see table below for details of time points for assessment)

## 6.1. Child characteristics

The following measures, selected to assess children's characteristics, are all widely used in the autism field and are of established reliability and validity.

*i) Autism symptoms:* The Social Communication Questionnaire - Lifetime version  is a brief parent/caretaker questionnaire that assesses the presence of autism symptoms *ii) Developmental level*: The Mullen Scales of Early Learning (MSEL)  provide a comprehensive standardised measure of motor, perceptual, and language abilities in children aged from birth to 68 months. Raw scores on each subscale will be transformed to age-normed *t*-scores.

*iii) Communication:* Communication Development Inventory  (CDI) Words and Gestures The parent rated version of this questionnaire, designed for typically developing children aged 8-18 months. Raw scores will be used to assess the understanding and use of vocabulary and nonverbal gestural signals. It will also be used at the end of intervention to explore whether there has been any overall change in children's communication skills. *iv) Adaptive Behaviour*: The Adaptive Behaviour Assessment System  (ABAS) which extends from birth to 89 years, is a measure of adaptive skills across 3 major domains: Conceptual, Social, and Practical.

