#### 6. Summary of assessment measures

The following table summarises the measures to be used at baseline, end of treatment and at short term follow-up:

Descriptive measures (baseline only)	Pre and post treatment measures	Post treatment only	Follow-up*
Social Communication Questionnaire	PECS usage (telephone App and video)	Assessment of parent treatment fidelity*	PECS usage* (telephone App and video)
Mullen Scales of Development	Communication Development Inventory (CDI)	Feedback on participation using Social Validity Questionnaire*	
Adaptive Behaviour Assessment System (ABAS)		Child and Adolescent Service Use Schedule (CA- SUS)	

\* treatment group only

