#### 9. STATISTICAL ANALYSIS

The similarity of data derived from the App and video will be compared to establish the respective value of these sources of data. Parental counts (via telephone App) and video recordings of number of spontaneous requests used by the child will be analysed using intention-to-treat approach in a mixed ANOVA model, accounting for clustering within school and covarying for baseline score on the same measure. This will inform the sample size for a possible full randomised control trial. A preliminary power calculation (2-tailed p=.05 and assuming 10% drop-out or failure of equipment) indicates that the study has 47% power, for an effect size of 0.5 and 62% power for an effect size of 0.6 on the secondary measure of rate of spontaneous requests using PECS. Change in vocabulary use (assessed by the CDI) will also be compared across groups. In addition we will explore the impact on outcome of child characteristics e.g. age, developmental level and parental fidelity to treatment as rated by the therapist (see measures).

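### Developmental level is to be scored as age-normed Mullen t-scores, but the stated test range ends at 68 months while children are eligible to 10 years, so the score cannot be computed for older children

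*Protocol*

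**What the plan says.** Section 6.1 of the protocol, under developmental level, names the Mullen Scales of Early Learning. It gives their coverage and fixes the scoring in one run: they measure abilities "in children aged from birth to 68 months. Raw scores on each subscale will be transformed to age-normed" t-scores. No exception or alternative is attached.

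Eligibility is wider. Section 5.2 has "Child: age between 2 and 10 years", and Section 5.4 repeats it as "a) age 2-10 years b) with a clinical diagnosis of autism spectrum disorder"; the study summary gives the same limits. The summary table of assessment measures lists "Mullen Scales of Development" among the baseline-only descriptive measures, with no age restriction.

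Two analyses draw on the information. Section 9 intends to "explore the impact on outcome of child characteristics e.g. age, developmental level" and therapist-rated parental fidelity. Section 5.3 says that any group differences in cognitive or other abilities will be explored in analysis.

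**The concern.** A t-score of this kind places a child against other children of the same chronological age. If the test covers ages only to 68 months, there is no reference group for a seven- or nine-year-old and no t-score to calculate. The protocol has therefore fixed a scoring rule that fails over much of its own eligible age range. This differs from leaving a detail to the statistical analysis plan.

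The loss would not be haphazard. Whether a child has a t-score would depend entirely on age, and age is itself one of the characteristics to be explored in Section 9. An analysis using both would keep only children of 68 months or younger. It could say nothing about developmental level in older children. The check on cognitive balance between groups foreseen in Section 5.3 would be cut down in the same way.

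**Working it through.** The plan gives no figure on this point to reproduce. The check compares two age ranges.

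**Inputs**
- Upper limit of the Mullen: 68 months (Section 6.1), which is 68/12 = 5.67 years, or 5 years 8 months.
- Eligible age: 2 to 10 years (Sections 3, 5.2 and 5.4). The lower limit is 24 months. The upper limit is 120 months if it means the tenth birthday, or 131 months if children up to 10 years 11 months are admitted. The protocol does not say which.
- Planned sample: 64 children (Section 5.2).
- Age distribution: not given.

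**Share of the eligible age range without a t-score**

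Share = (upper age limit − 68) / (upper age limit − 24).
- Upper limit 120 months: (120 − 68)/(120 − 24) = 52/96 = 54%.
- Upper limit 131 months: (131 − 68)/(131 − 24) = 63/107 = 59%.

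The t-score is thus available over 44 of 96 months (46%) or 44 of 107 months (41%).

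**From age range to children**

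This step needs the age mix. Purely as an illustration, if ages were spread evenly over the range, the planned sample would contain 64 × 52/96 = 34.7, or 64 × 63/107 = 37.7, children without a t-score, which is about 35 to 38. Without that assumption the number could lie anywhere from 0 to 64.

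**Is the gap closed elsewhere?**

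The neighbouring measures in Section 6.1 make a useful comparison.

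| Measure | Stated age range | Stated score | Usable from 2 to 10 years? |
|---|---|---|---|
| CDI Words and Gestures | 8–18 months (typically developing children) | Raw | Yes, needs no norms at the child's age |
| ABAS | Birth to 89 years | Not stated | Yes, range covers all eligible ages |
| Mullen | Birth to 68 months | Age-normed t-score | Only up to 68 months |

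The age limit is dealt with for the CDI, by raw scores, and does not arise for the ABAS. Only the Mullen has an age-normed score prescribed beyond its stated range.

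**The case against.** The strongest reply is that little depends on the t-score, and most of that reply stands. The Mullen is a baseline-only descriptor. It is not an eligibility criterion or a randomisation stratifier, and it is not named among the outcomes in Section 8 (though the general completion of assessments is a feasibility outcome there). The covariate in the Section 9 model is the baseline value of the same outcome measure. The analyses that would use developmental level are exploratory, in a pilot with stated power of 47% to 62%. Section 9 also speaks of developmental level, not of t-scores, so an analysis plan could define the variable differently. The ABAS gives a related functional measure at every eligible age. These points limit the harm, but they leave Section 6.1 prescribing a score that older children cannot have.

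A second reply is that Section 5.4 expects low developmental ages: "The developmental age equivalent of children eligible for the study is likely to be below 18 months of age". That may justify giving Mullen items to older children. It supplies no norms at their chronological age, so it does not rescue the t-score.

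A reader might infer three stronger things that the documents do not support:
- **That developmental level is lost altogether for older children.** Only the t-score is lost. Raw scores are collected for every child.
- **That 54% to 59% of children lack a score.** The figures describe the age range, not the sample.
- **That t-scores are also nearly useless within range, because all children sit at the floor of the norms.** This needs the norm tables, which the protocol does not contain. Section 5.4 says only that a developmental age below 18 months is likely, in a discussion of capacity to assent. For a child of 24 months, an age equivalent just under 18 months is about 18/24 = 75% of chronological age, and nothing in the protocol shows that to be the extreme low end.

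**Conclusion.** The point holds for the t-score in children over 68 months. Sections 5.2 and 6.1 cannot both be followed: the prescribed score does not exist over 54% of the eligible age range, or about 59% on the wider reading of 10 years. This rests on the protocol's own statement of the Mullen's coverage and on the fact that an age-normed score requires norms at the child's chronological age. How many children are affected cannot be determined from the document.

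The consequence is a loss of older children from two exploratory analyses, determined by age. Severity is moderate to minor. No primary or secondary outcome, treatment comparison or sample-size input depends on this score, but the rule fails as written and is easily corrected.

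**What to change.** Replace the t-score sentence in Section 6.1 with one stating that Mullen raw scores or age equivalents will be used for every child, since neither needs norms at the child's chronological age. State in Section 9 that this variable, together with age, enters the exploratory analyses, and use the same variable for the comparison of groups foreseen in Section 5.3. T-scores may be reported in addition for children up to 68 months, labelled as a subset.

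The cost is one sentence in Section 6.1 and a short clarification in Section 9. The raw scores are already part of the baseline assessment, so no child needs re-testing, and the change can be made although recruitment has closed. The drawback is that raw scores and age equivalents are not adjusted for age: an older child will tend to score higher at the same relative level. Age must therefore be in the model, and the developmental-level estimate read as conditional on age.

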#### 6.2. PECS usage

PECS is specifically designed to increase spontaneous communication and our focus is on the feasibility of assessing truly spontaneous requests (i.e. unprompted by a task or context) in the home. Changes in such behaviours cannot easily be captured in a short assessment session and recordings made by an unknown observer in the home are likely to interfere with natural communication. Thus, we aim to acquire parent rated and independent verification of the frequency and types of spontaneous requests made by the child at home using two novel approaches to data collection:

a) App for use on smartphones (i.e. Tally Tracker App). Parents will be asked to use the App supplied by the research team, to make frequency counts of: a) requests made using PECS; b) requests made by other means (e.g. speech, vocalisations or gestures etc.);. Any other forms of communication will be recorded in an 'other' category as qualitative data.

The researcher will provide the app and assist all participants in downloading it on their mobile phones. Two app step-by-step guides (i.e. for iPhone and android) will also be given to parents. The app is easy to use and does not involve complex features. Use of the App at these pre-specified times will be prompted by a text from the research assistant [name].

- b) Video recording using a very small body camera (approximately 4cm x 2cm), worn by the child (as used by cyclists; see appendices). This equipment will provide corroborative information about the frequency and type of spontaneous communication used by the child at home. Personal communication from two parents who were asked to use the cameras and report back to the study team (one typically developing child and one with autism) have confirmed acceptability after a short period of acclimatisation details). Families will be given a defunct camera prior to the recording sessions in order to allow the child to become comfortable with the device. Cameras will be supplied via the research team. A step-by-step guide on how to use the camera will be provided to parents. All data will be removed from the camera and stored on an encrypted hard drive by a designated member of the study team.
- c) Use an App provided by the research team (i.e. Tally tracker App) on their mobile phones in order to record the number and type of requests that their child makes over two specified periods as follows: 1) for 2-3 hours on a weekday after school and 2) for 2-3 hours at a weekend. This data will be collected at three time points during the duration of the study (i.e. pre and post treatment and follow-up) for both groups (i.e. TAU and treatment groups). The researcher will provide the app and assist all participants in downloading it on their mobile phones. The app is easy to use and does not involve complex features.
- d) Attach a small video camera (approximately 4cm x 2cm) similar to that used by cyclists and provided by the study team, to their child's clothing to provide direct observations about the frequency and type of spontaneous communication used by the child at home.

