## 5. Short-term follow-up (Intervention group only)

Previous studies have indicated that PECS use is not maintained once direct intervention has ceased . Thus, approximately one month post-treatment, use of PECS at home will be assessed using the App and cameras (as described above) to determine whether families have continued to use the intervention once they are no longer actively involved in therapy and to see if progress by the child has been sustained.

Table 1 summarises the measures to be used at baseline, end of treatment and at short term follow-up.

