## 8. STUDY OUTCOMES

As this study is designed as a feasibility study primary outcome data will focus on the following variables:

- a) Successful recruitment strategy i.e. recruitment of 64 eligible participants
- b) Data collection on questionnaire and direct assessments for all participants at each assessment time point
- c) Utility of the App and body-worn cameras and quality of data obtained from this equipment.
- d) Retention of families in both groups,
- e) Number of home-based sessions delivered by the therapist
- f) Evaluation of the PECS stages established for treatment families (parent treatment fidelity)
- g) Child and Adolescent Service Use Schedule (CA-SUS) to ascertain local provision
- h) Parent, teacher, research assistant and therapist feedback on feasibility and acceptability (Social Validity Questionnaire, focus groups).

The secondary outcome data will focus on the following:

a) PECS usage - (telephone App and video). The RA will extract frequency counts from the App and score episodes of requesting from films (remaining blind to group allocation).

Experience of coding behaviour from video suggests that it should be possible to scroll through the video at a medium-fast forward pace to identify episodes of requesting behaviour and then to score them according to 2 codes: 1) use of PECS, 2) other forms of request (e.g. speech, vocalisations or gestures etc.)

b) Communication Development Inventory (CDI) to explore whether there has been any overall change in children's communication skills.

Additional outcome data:

a) A short anonymous questionnaire to explore children's access to PECS intervention from professionals working with children with autism. The questionnaire will be circulated through professional Clinical Excellent Networks (CENs) via Survey Monkey. It is designed to take under 10 minutes to complete, consisting mainly of multiple choice questions.

b) A short anonymous questionnaire to ascertain if individuals transferring to adult services do so with some skills using PECS and also to establish if PECS is included in treatment for adults. The questionnaire will be sent through professional Clinical Excellence Networks (CENs) to professionals working in adult therapy services via Survey Monkey. It takes under 10 minutes to complete and is mainly comprised of multiple choice questions.

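### The protocol gives two versions of who is assessed at follow-up; the treatment-only version has no comparator and could let the blinded research assistant infer allocation

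*Protocol*

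**What the plan says.** **Who is followed up.** Section 6.2, item c), lists App counts at three time points: "i.e. pre and post treatment and follow-up) for both groups (i.e. TAU and treatment groups". Item d), on the body camera, names neither time points nor groups.

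Later in the assessments chapter a section is headed "Short-term follow-up (Intervention group only". It states that "approximately one month post-treatment, use of PECS at home will be assessed using the App and cameras (as described above". In the summary table of assessment measures, the pre and post entry "PECS usage (telephone App and video") carries no asterisk. The follow-up column heading and its PECS usage entry both do, and the footnote reads "treatment group only".

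**What follow-up is for.** Section 5.1, aim (f), is a follow-up four weeks after training ends, "to monitor the continuing use of PECS at home and any sustained progress made by the child".

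**Who handles the data.** Sections 5.3 and 5.4 keep the research assistant blind to allocation. Section 5.4 adds that, once randomised, parents are given the number of an unblinded team member. Section 6.2, item a), nevertheless says: "Use of the App at these pre-specified times will be prompted by a text from the research assistant". Section 8 has the same assistant extract the App counts and "score episodes of requesting from films (remaining blind to group allocation").

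**What is counted.** Primary outcome (b) in Section 8 is data collection for all participants at every assessment time point. The planned sample in Section 5.3 is 64, with 32 per group.

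**The concern.** Which families are assessed, and when, is protocol content, and here it is fixed in two incompatible ways. Staff working from Section 6.2 would contact TAU families at follow-up; staff working from the table would not.

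Three things depend on the answer:

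- **Comparator.** Without TAU data at follow-up, a child's request count cannot be separated from maturation, school provision or repeated measurement.
- **Blinding.** The parents' App counts are unblinded, and Section 6.2 relies on the video for independent verification. A follow-up list made up only of treatment families shows the person sending the prompts who was allocated to PECS.
- **Denominator.** Completeness at follow-up, part of primary outcome (b), has no fixed base.

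**Working it through.** **1. The passages side by side**

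| Place in protocol | App at follow-up | Camera at follow-up |
|---|---|---|
| Section 6.2, item c) | both groups | not addressed |
| Section 6.2, item d) | not addressed | no time point or group given |
| Short-term follow-up section | intervention group | intervention group |
| Summary table | treatment group | treatment group |

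The direct conflict concerns the App. For the camera, only the restricted version is stated.

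**2. Does anything else settle it?** The heading of Section 6 sends the reader to the table for time points, which favours the restricted version. It does not remove the sentence in Section 6.2 that names both arms. The COVID-19 deviations in Sections 15.1 and 15.2 mention follow-up assessments without naming a group.

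**3. The protocol's power figure.** Section 9 states 47% power at an effect size of 0.5 and 62% at 0.6, two-sided 0.05, with 10% loss.

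- Evaluable: 64 × 0.9 = 57.6, so n = 28.8 per arm.
- Power ≈ Φ(d√(n/2) − 1.96).
- d = 0.5: 0.5 × √14.4 = 1.897; Φ(−0.063) = 47.5%.
- d = 0.6: 0.6 × √14.4 = 2.277; Φ(0.317) = 62.4%.

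The stated figures reproduce. Section 9 does not say which time point they refer to, so they do not resolve the conflict.

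**4. What each version yields at follow-up (planned numbers)**

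| Version | Treatment | TAU | Denominator | Between-group estimate |
|---|---|---|---|---|
| Both groups (App) | up to 32 | up to 32 | 64 | possible; about 29 v 29 after 10% loss |
| Treatment only | up to 32 | 0 | 32 | none |

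**5. The route to unblinding.** This is an inference from stated duties; the protocol does not say it.

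- The assistant prompts App use at the scheduled times.
- The follow-up section uses the App in the way already described.
- Under the restricted version, a family prompted at follow-up is therefore a treatment family, and a family that is passed over is a TAU family.

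Exposure starts at follow-up contact. Baseline and post-treatment films scored before then are unaffected. Follow-up material, and post-treatment films still waiting to be scored, are exposed. Section 8 sets no order of scoring. Section 15.1 shows schools at different stages at the same date, so contact and scoring may overlap.

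**The case against.** The strongest reply is that the protocol points to its own governing source. The Section 6 heading refers to the table, the table and the follow-up section agree, and item c) of Section 6.2 is the outlier. Items c) and d) there largely repeat items a) and b) and have no lead-in, so they may be misplaced text. This makes treatment-only the likelier intention. It still leaves a sentence in force that says otherwise, with no rule of precedence.

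Second, aim (f) is to monitor, and whether families go on using PECS after therapy stops is a question about the treated arm. Section 9 specifies no between-group contrast at follow-up. That stands: a one-arm follow-up is defensible in a feasibility trial if it is called descriptive. A reader might infer that aim (f) is then unanswerable. Only the attribution of sustained child progress to the intervention is out of reach.

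Third, a reader might infer that the video outcome loses its blinding. The document does not show this. It gives no scoring schedule, Section 5.4 takes deliberate steps to protect the assistant, and films scored before follow-up contact are safe. The risk is conditional.

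Fourth, a reader might take Section 6.2 to promise camera follow-up in TAU as well. It does not: the both-groups statement covers the App alone.

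Finally, the randomised pre/post comparison does not depend on which version applies, except through any post-treatment film scored late.

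**Conclusion.** The contradiction is explicit in current text and needs no inference. Its size on planned numbers is a follow-up denominator of 64 or 32, and a follow-up comparison of up to 32 v 32 or of 32 v 0. Achieved numbers may be smaller, since Section 15.2 records that recruitment closed on 12/01/2021.

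Under the restricted version two consequences follow. Sustained progress can only be described within the treated arm. And App or film data that the research assistant handles after follow-up contact would not be reliably blind. The second assumes that the assistant sends the follow-up prompts, as Section 6.2 implies, and it matters for the randomised comparison only if post-treatment films remain unscored at that point. The documents do not establish that blinding was in fact lost, or that the pre/post comparison is compromised.

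**What to change.** State one version in Section 6.2, the short-term follow-up section and the summary table.

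- **Option (i), both groups.** Collect follow-up App counts in both arms, timed from a matched end-of-treatment date, and report the between-group contrast. Camera follow-up in TAU would be an addition to the plan and should be described as one.
- **Option (ii), treatment only.** Limit aim (f) to describing continued PECS use and within-arm change, and set the follow-up denominator for primary outcome (b) at 32.

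Under either option:

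- Have the unblinded team member from Section 5.4 arrange follow-up and send its prompts.
- Leave App extraction and film scoring with the blinded assistant. Passing extraction to an unblinded person would remove a safeguard that Section 8 specifies.
- Score post-treatment films before follow-up contact, or with identity and time point masked.

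**Cost.** Option (ii) is wording and a change of who sends texts. Option (i) adds one App round for up to 32 TAU families. With two recording periods of 2–3 hours each, that is 4–6 hours of parent counting per family, which Section 6.2 already asks for. It cannot be applied retrospectively: Section 15.1 lists the first school's assessments as completed. Where follow-up has already taken place, record which version was applied and when the films were scored.
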